1.2 SCHEMA

- a Two target lesions with a difference no greater than 1 point in total sign scores (TSS) will be randomly assigned in an intra-patient manner 1:1 to PRN473 Gel, 5% or matching placebo. The two target lesions will be dosed twice daily at study site during the Blinded Period with the second dose application approximately 12 hours after previous dose. The investigational products could be applied by a trained medical professional at patient's home or an external clinic, where available, as a backup option.
- b During the Open Label Period, patients will apply PRN473 Gel, 5% BID to the all AD-affected areas, except the scalp, palms, soles, and genitals and should continue to treat the assigned areas throughout the Open Label Period.

1.3 SCHEDULE OF ACTIVITIES (SOA)

Product Name: PRN473 (SAR444727)

			Tre	eatment Period	(Days 1-42)				
Screening		(at site/home/o staff-admi	d Period ^a study external clinic inistered BID Days 1-14)	(BID dosi	Open-Lab ng at home b		ys 15-42)	End of Study/Early Termination	Safety Follow-up Phone Call
Assessment	Days -35 to -1	Day 1 (Baseline)	Days 2-14	Day 15 (+2 days)	Day 18 (±2 days)	Day 29 (±2 days)	Day 36 (±2 days)	Day 43 (±2 days)	Day 56 (±2 days)
Informed consent	X								
Eligibility check	X	X b							
Medical history	X	X b							
Demographics	X								
Physical examination d	X	X b	X c	X		X		X	
Height (screening only), weight	X	X b							
Serum pregnancy test	X								
Urine pregnancy test ^e		X b				X		X	
Clinical laboratory tests	X	X b		X		X		X	
Serology (HIV, hepatitis B and C) and TB test	X								
FSH ^f	X								
Urinalysis	X	X b		X		X		X	
12-lead ECG	X	X b						X	
Vital signs ^g	X	X b	X c	X		X		X	
Telemedicine visit h					X		X		
EASI ^b		X		X		X		X	
vIGA-AD ⁱ	X			X b		X b		X b	
Evaluation of treatable BSA	X			X		X		X	
Lesional TSS	X	X b	X c	X b		X b		X b	

Principia Biopharma, Inc. Confidential and Proprietary 22 of 100 01-Mar-2022 Final

			Tre	eatment Period	l (Days 1-42)				
	Screening	(at site/home/e staff-admi	d Period ^a study external clinic nistered BID Days 1-14)	(BID dosi	Open-Lab ng at home b		ys 15-42)	End of Study/Early Termination	Safety Follow-up Phone Call
Assessment	Days -35 to -1	Day 1 (Baseline)	Days 2-14	Day 15 (+2 days)	Day 18 (±2 days)	Day 29 (±2 days)	Day 36 (±2 days)	Day 43 (±2 days)	Day 56 (±2 days)
Randomization		X b							
POEM ^b		X		X		X		X	
Selection of the lesions	X								
Lesional PP-NRS ^j		Days	s 1-14 ^b	X ^b					
Lesional vIGA k		X b	Х°	X ^b					
DLQI ^b		X		X		X		X	
SCORAD ^b				X		X		X	
PP-NRS ^b					Days 1	5-42		X	
Photographs ¹		X b	X °	X b		X b		X	
Study intervention dosing		X u	X ^u	X m		X n			
Study intervention distribution				X		X			
Study intervention dosing at home					Days 1	.5-42 n			
Daily patient diary °					Days 1	5-42			
Study intervention collection/review						X		X	
Skin biopsy collection		X b		X		X ^p			
Suture removal, if applicable				X				X	
Skin tape stripping ^q		X b	X °	X b		X b		X	
PK blood sampling ^r		X	Χ°	X		X		X	
Blood biomarker levels ^s		X b	Х°	X				X	
Application site tolerability assessment t		X	X	X		X			

Principia Biopharma, Inc. Confidential and Proprietary 23 of 100 01-Mar-2022 Final

			Treatment Period (Days 1-42)						
	Screening	(at site/home/e staff-admi	d Period ^a study external clinic nistered BID Days 1-14)	(BID dosi	Open-Lab ng at home b	el Period y patient Day	ys 15-42)	End of Study/Early Termination	Safety Follow-up Phone Call
	Days -35	Day 1	Days 2-14	Day 15	Day 18	Day 29	Day 36	Day 43	Day 56
Assessment	to -1	(Baseline)		(+2 days)	(±2 days)	(±2 days)	(±2 days)	(±2 days)	(±2 days)
Prior and concomitant medication review			ongoing from screening					X	X
AE reporting	ongoing	from the time of	of consent (non-tr	reatment- and tr	eatment-emer	gent adverse	events)	X	X

Abbreviations: AE = adverse event; BSA = body surface area; DLQI = Dermatology Life Quality Index; EASI = Eczema Area and Skin Severity Index; ECG = electrocardiogram; FSH = Follicle-stimulating hormone; IGA = Investigator Global Assessment; PK = pharmacokinetic; POEM = Patient-Oriented Eczema Measure; PP-NRS = Peak Pruritus Numeric Rating Scale; SCORAD = SCORing atopic dermatitis; TSS = total sign score; vIGA-AD = validated Investigator Global Assessment-Atopic Dermatitis.

Schedule of Activities (SoA), continued

- a During the Blinded Period, patients will come into the study site twice daily for drug application (approximately 12 hours after the previous dose) and collection of adverse events. The investigational products could be applied by a trained medical professional at patient's home or an external clinic, where available, as a backup option.
- b Procedure performed predose.
- c Procedure performed prior to the morning dose on Day 8.
- d A complete physical examination is to be performed at the Screening and End of Study visits. A symptom-directed physical exam is to be performed as clinically indicated at other visits.
- e A positive urine pregnancy test must be confirmed by a serum test.
- f For post-menopausal women of non-childbearing potential only.
- g On Days 1, 8, and 15, vital signs are measured predose.
- h During the telemedicine visits on Days 18 and 36, drug application, patient questions about daily diary, new or changed AEs, and new or changed concomitant medications will be reviewed with the patient.
- i The vIGA-AD will be conducted predose on all treated lesions at screening, Day 15, 29 and 43 during Open Label period.
- j The lesional PP-NRS will be administered predose separately on each of the 2 target lesions only during Blinded Period and predose at Day 15.
- k The lesional vIGA-AD will be administered predose separately on each of the 2 target lesions only during Blinded Period and predose at Day 15.
- I Photographs will be used to document change/improvement in lesions, and to document biopsy location and will not be used to evaluate adverse events. For the Blinded Period, photographs will be taken of the 2 target lesions predose at Baseline and Day 8. For the Open-Label Period, photographs of the 2 target lesions will be taken predose at Day 15, Day 29 and at Day 43.
- m Study intervention dosing on the morning of Day 15 will be applied by the patient under the instruction of the site staff.
- n Study intervention dosing on the evening of Day 15 and on Days 16-42 will be applied by the patient at home. Day 29 visit dosing will be done after predose assessments at study site. The EOS visit (Day 43) should occur approximately 12 hours after the previous dose.
- Daily diaries will collect the patient reported PP-NRS.
- p Skin biopsy at Day 29 is optional.
- q Skin tape stripping (STS) will be performed predose on Days 1, 8 (optional), 15, 29, and at Day 43 for the two target lesions, and on Day 1 for the normal skin.

Principia Biopharma, Inc. Confidential and Proprietary 24 of 100 01-Mar-2022 Final

Clinical Study Protocol PRN473-0005 (ACT17131)

- r PK samples will be collected at the following timepoints relative to the morning dose: predose and at 1, 4, and 6 hours postdose on Days 1 and 15; predose on Days 8 and 29; and at the Day 43 visit, approximately 12 hours after the last dose of study intervention. The time of last application of study intervention prior to the Day 8, Day 15, Day 29, and Day 43 visits should be recorded. The allowed time deviation window before a deviation is recorded for blood sample collection post dose is 15 minutes for time points up to and including 6 hours post dose; pre-dose samples should be collected within 30 minutes prior to the next application of study intervention.
- s Samples for blood biomarker levels should be drawn predose on Days 1, 8 and 15, and at the Day 43 visit approximately 12 hours after the last dose of study intervention.
- t Local tolerability assessment will be performed within approximately 30 minutes of dosing by site staff using the symptom grading in Appendix 4 (Section 10.4.1) at each dosing when patients are at study site during dosing. During the blinded period in case the investigational products are applied at the patient's home or external clinic, the local tolerability assessment will be performed by a trained medical professional, different than the person administering the study intervention.
- u If it becomes difficult for the patient to visit the study site, investigational products could be applied by a trained medical professional at patient's home or an external clinic, where available, as a backup option. The morning Visit of D1 and D8 must be conducted at the study site.

Principia Biopharma, Inc. Confidential and Proprietary

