4.3 JUSTIFICATION FOR DOSE

Product Name: PRN473 (SAR444727)

The dose of PRN473 selected for topical administration during the Blinded Period on Days 1-14 in PRN473-0005 (ACT17131) is PRN473 Gel, 5% or matching placebo at approximately 2.5 mg/cm² over a 100 cm² area encompassing each target lesion BID (approximately 12 hours apart). During the Open-Label Period on Days 15-42, PRN473 Gel, 5% at 2.5 mg/cm² will be applied BID to all AD-affected areas excluding the scalp, palms, soles, and genitals over a body surface area of up to 14%. This dose is in the range of those associated with biological activity based on preclinical disease models and is therefore considered appropriate to evaluate in this initial assessment of PRN473 Gel efficacy in patients with AD.

The proposed dosing regimens are supported by clinical safety data from the PRN473-0002 study. The total daily dose during the Blinded Period of the study (25 mg PRN473 active pharmaceutical ingredient [API] per day) is approximately 7-fold lower than the daily dose applied in the multiple dose arm of PRN473-0002 (175 mg PRN473 API per day). This dose was safe and well-tolerated and there were no serious adverse events (SAEs) or AEs that led to discontinuation.

In the Open-Label Period, the dosing regimen of PRN473 5% (w/w) gel at 2.5 mg/cm² gel over 14% BSA BID will provide a daily PRN473 (API) dose of 665 mg to a patient with a total body surface area of 1.9 m². This is less than the dose of 700 mg PRN473 (API), which was the highest dose administered in the PRN473-0002 single ascending dose/multiple dose study in healthy participants. This dose was safe and well-tolerated and there were no SAEs or AEs that led to discontinuation.

Patients will measure the dose by the fingertip unit method and the expected dose variability when the compound is topically self-applied by this method may be up to two-fold excess of compound which is reasonably below the safety margin.

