5.1 INCLUSION CRITERIA

Patients are eligible to be included in the study only if all the following criteria are met:

- 1. Male and female adults 18 to 70 years of age (inclusive) at the time of informed consent.
- 2. Diagnosed with mild to moderate AD, meeting at least 3 major and 3 minor criteria according to Hanifin and Rajka (Hanifin 1980; Appendix 4, Section 10.4.4) prior to or at the Screening visit.
- 3. History of AD for at least 6 months as determined by the Investigator through patient interview.
- 4. Stable disease for the 4 weeks prior to the screening visit with no significant flares in AD as determined by the Investigator.
- 5. Validated Investigator Global Assessment-atopic dermatitis (vIGA-AD) score of Moderate (3) or Mild (2) at Screening. The vIGA-AD is evaluated for the entire body except scalp, palms, soles and genitals.
- 6. Has AD involvement (excluding scalp, palms, soles and genitals) of at least 1.0% BSA and no more than 14.0% BSA.
- 7. Has at least two target lesions 100 cm² or greater with a difference no greater than 1 point in lesion TSS and at least 5 cm apart located on the trunk (excluding genitals) or upper extremities (excluding palms)
- 8. Male patients are eligible to participate if they agree to the following during the intervention period and for at least 2 days (eg, 5 terminal half-lives) after the last dose of study intervention,
- Refrain from donating sperm

PLUS, either:

- Be abstinent from heterosexual intercourse as their preferred and usual lifestyle (abstinent on a long term and persistent basis) and agree to remain abstinent.

OR

Must agree to use contraception/barrier as detailed below:
 Agree to use a male condom and an additional highly effective contraceptive method as described in Appendix 2 Contraceptive and barrier guidance (Section 10.2) when

having sexual intercourse with a woman of childbearing potential (WOCBP) who is not currently pregnant.

- 9. A female patient is eligible to participate if she is not pregnant or breastfeeding, and one of the following conditions applies:
- Is a WONCBP as defined in Appendix 2 Contraceptive and barrier guidance (Section 10.2).

OR

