Patients are required to apply an emollient (except urea-containing or medicated emollients that are regulated as medical device) daily from Day -7 to Day 1. Beginning on Day 1, emollient is to be applied only on untreated areas (eg, may not be used on the 2 target lesions during Days 1-14, and may not be used on any parts of the body being treated with PRN473 Gel, 5% during Days 15-42).

PRN473 Gel, 5% or matching placebo will be removed from storage at 2-8°C and held at room temperature for at least 30 minutes prior to administration. Site staff or trained medical professional will apply PRN473 Gel, 5% or matching placebo with nitrile gloves to the 2 target lesions per the randomization assignment, as follows:

- Approximately 2.5 mg gel/cm² to each 100 cm² target lesion on Days 1-14. If the target lesion is less than 100 cm², the application area should include surrounding nonlesional skin; if the target lesion is larger than 100 cm², only 100 cm² of the lesion should be marked and treated.
- On Days 15-42 (open-label period), patients are instructed to apply PRN473 Gel, 5% BID to all AD-affected areas in a thin layer, excluding the scalp, palms, soles, and genitals.

Under no circumstances will the Investigator supply study intervention to a third party (except for direct to patient [DTP] shipment or direct to designated clinic for home health care option if patient is not able to be dosed at home, for which a courier company has been approved by the

Sponsor), allow the study intervention to be used other than as directed by this clinical trial protocol, or dispose of study intervention in any other manner.

Intervention units are returned by the patient at each visit. In case of DTP process, the intervention units can be returned by the carrier (if defined in the contract).

Further details will be outlined in the Pharmacy Manual.

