8.1 EFFICACY ASSESSMENTS

Efficacy assessments will be performed per the Schedule of Assessments in Section 1.3:

- Lesional PP-NRS is a patient-completed assessment to determine the intensity of lesion pruritus.
- Lesional validated IGA is an Investigator assessment of the 2 target lesions during the Blinded Period and predose at D15 during the Open-Label Period.
- Eczema Area and Skin Severity Index (EASI) is a validated Investigator-administered scoring system used to measure the severity of clinical signs in AD.
- Validated Investigator Global Assessment-Atopic Dermatitis (vIGA-AD; Appendix 4, Section 10.4.2) is an Investigator assessment of the global severity of clinical signs in AD.
- Lesion TSS (Appendix 4, Section 10.4.3) is a scale that rates the severity of each of 4 AD symptoms (erythema, induration/papulation, excoriation, and lichenification) on a 4-point scale from 0 (none) to 3 (severe), for a total score ranging from 0 to 12.

- SCORing atopic dermatitis (SCORAD) is a clinical tool used to assess AD by intensity, extent, and subjective signs.
- Peak Pruritus Numeric Rating Scale (PP-NRS) is a patient-completed assessment to determine the intensity of peak pruritus over the previous 24 hours.
- Patient-Oriented Eczema Measure (POEM) is a validated, patient-derived assessment measure for monitoring atopic eczema severity.
- Dermatology Life Quality Index (DLQI) is a validated, self-administered questionnaire designed to measure the health-related quality of life of adult patients suffering from a skin disease.
- Estimation of treatable BSA.

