 - Proportion of participants with at least a reduction $\geq 50\%$ in EASI (EASI-50), with at least a reduction $\geq 75\%$ in EASI (EASI-75), with at least a reduction $\geq 90\%$ in EASI (EASI-90), and with at least a reduction $\geq 100\%$ in EASI (EASI-100), from Baseline to Days 15, 29 and 43
 - Proportion of participants with EASI-50, EASI-75, EASI-90, and EASI-100 from Day 15 to Days 29 and 43
- For v-IGA-AD
 - Proportion of participants achieving vIGA-AD of 0 (clear) or 1 (almost clear) at Day 29

- Proportion of participants achieving a vIGA-AD of 0 (clear) or 1 (almost clear) at Day 43
- Proportion of participants achieving vIGA-AD of 0 (clear) or 1 (almost clear) and a reduction of ≥ 2 points from Day 15 to Day 29
- Proportion of participants achieving vIGA-AD of 0 (clear) or 1 (almost clear) and a reduction of ≥ 2 points from Day 15 to Day 43
- For Body Surface Area (BSA)
 - Change from Day 15 in percentage of treatable BSA at Days 29 and 43
- For Scoring Atopic Dermatitis (SCORAD)
 - Percent change from Day 15 in SCORAD index at Days 29 and 43
- For Patient Oriented Eczema Measure (POEM)
 - Change from Baseline in POEM at Days 15, 29, and 43
 - Change from Day 15 in POEM at Days 29 and 43
 - Proportions of participants with a reduction in POEM ≥ 4 from Baseline at Days 15, 29 and 43 in participants with POEM ≥ 4 at Baseline
 - Proportions of participants with a reduction in POEM ≥ 4 from Day 15 at Days 29 and 43 in participants with POEM ≥ 4 at Day 15
- For Dermatology Quality of Life Index (DLQI)
 - Change from Baseline in DLQI at Days 15, 29, and 43.
 - Change from Day 15 in DLQI at Days 15, 29, and 43
 - Proportions of participants with a reduction in DLQI ≥ 4 from Baseline at Days 15, 29 and 43 in participants with DLQI ≥ 4 at Baseline
 - Proportions of participants with a reduction in DLQI ≥ 4 from Day 15 at Days 29 and 43 in participants with DLQI ≥ 4 at Day 15

Analyses for binary endpoints

The binary endpoints will be descriptively summarized using number, percentage and 95% confidence interval (CI) of percentage at each time point.

The proportion of subjects meeting the binary endpoint during the Open label period and corresponding exact 95% and 80% CI (95% CI and 80% CI respectively calculate with Wilson score method) will be summarized.

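### vIGA-AD is defined on two different skin areas, so the Day 15 reference for the open-label response could be rated on other skin than Days 29 and 43

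*Protocol*

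**What the plan says.** **Two definitions of the rated area.** Criterion 5 (protocol Section 5.1, also in the synopsis) says: "The vIGA-AD is evaluated for the entire body except scalp, palms, soles and genitals". Footnote i to the Schedule of Activities (Section 1.3) says: "The vIGA-AD will be conducted predose on all treated lesions at screening, Day 15, 29 and 43 during Open Label period". The SAP names no area for vIGA-AD.

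**What is treated, and when.** In the Blinded Period only the two target lesions receive gel, one active and one placebo. Section 6.2 gives the quantity: "Approximately 2.5 mg gel/cm² to each 100 cm² target lesion on Days 1-14". From Day 15 patients are told to "apply PRN473 Gel, 5% BID to all AD-affected areas in a thin layer, excluding the scalp, palms, soles, and genitals".

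**A separate lesional score.** Footnote k says: "The lesional vIGA-AD will be administered predose separately on each of the 2 target lesions only during Blinded Period and predose at Day 15".

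**The endpoint.** The schedule places vIGA-AD at Screening and Days 15, 29 and 43, and not on Day 1. The SAP (Section 3.4) lists "Proportion of participants achieving vIGA-AD of 0 (clear) or 1 (almost clear) and a reduction of" two points or more from Day 15, once for Day 29 and once for Day 43. It also lists the proportions at grade 0 or 1 on Days 29 and 43, with no Day 15 reference.

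**The concern.** What counts as a treated lesion changes during the study. There are none at screening, two before dosing on Day 15, and from then on all affected skin outside the four excluded sites. A rater who follows footnote i to the letter would grade the reference on one area and the outcome on another, and the 2-grade reduction would compare scores that do not describe the same skin.

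A rater has reason to follow the footnote. Protocol Section 8 makes adherence to the schedule a requirement. The amendment history (Section 10.5) records that the treated-lesion wording was adopted as a clarification, so it does not look like a slip that a site may ignore.

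The area can also move the grade. Appendix 4 (Section 10.4.2) settles indeterminate cases by extent and describes grade 4 as widespread disease.

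The Open-Label Period has no control arm in which the same shift would cancel. Its data may also enter the interim analysis that can end the study (protocol Section 9.5, SAP Section 3.8).

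**Working it through.** The plan gives no figure for this mismatch. The check is a comparison of areas, followed by the arithmetic of the response rule.

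**1. Inputs**
- Example body surface: 1.9 m² = 19,000 cm² (Section 4.3).
- AD involvement allowed: 1.0% to 14.0% BSA (criterion 6).
- Area treated before Day 15: 2 × 100 cm² = 200 cm² (Section 6.2), which is 200 / 19,000 = 1.05% BSA.

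**2. Check of the inputs against the plan's own dose figure.** 0.14 × 19,000 cm² = 2,660 cm². Then 2,660 × 2.5 mg/cm² × 5% × 2 applications = 665 mg per day, which is the figure in Section 4.3.

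**3. Share of the later area covered by a literal Day 15 rating.** Share = 200 / (BSA fraction × 19,000), capped at 1.

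| Affected BSA | Later area (cm²) | Share rated at Day 15 |
|---|---|---|
| 14% | 2,660 | 7.5% |
| 10% | 1,900 | 10.5% |
| 5% | 950 | 21% |
| 2% | 380 | 53% |
| 1% | 190 | all (capped) |

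**4. What the Day 15 grade does to the response rule** (grade 0 or 1, and a drop of at least 2)

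| Day 15 grade | Later grades that count as response |
|---|---|
| 0 or 1 | none |
| 2 | 0 only |
| 3 or 4 | 0 or 1 |

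**5. The shift can go either way.** Take a patient at grade 1 on Day 29.
- All treatable skin is grade 3 on Day 15 and the two targets are grade 2. The patient responds on the wide area (3 to 1) but not on the literal one (2 to 1).
- All treatable skin is grade 2 and the two targets are grade 3. The patient does not respond on the wide area (2 to 1) but does on the literal one (3 to 1).

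These two cases are illustrations. The documents give no data on how target lesions grade relative to the rest of the skin.

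**The case against.** The strongest reply is that the literal reading is not what the authors meant.
- The footnote applies the same words to screening, where they cannot mean skin already dosed.
- Footnote k already provides a separate rating of the two targets before dosing on Day 15, so the literal reading would rate the same two lesions twice at one moment.
- Section 8.1 separates the lesional score from vIGA-AD, which it describes as a measure of global severity.
- Footnote i places Day 15 in the Open-Label Period, when all affected skin outside the four sites is treated. On that reading it largely agrees with criterion 5.

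This stands as evidence of intent. It does not remove the conflict in the operative text, and nothing in the documents tells sites which definition prevails.

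Three stronger readings are tempting but not supported.
- *The Day 15 reference is biased low because the targets have improved.* One target received placebo, and nothing shows that the targets grade lower than the other skin. The direction is unknown.
- *New lesions are left out at Days 29 and 43.* Patients treat all affected areas, so a new lesion can be read as treated. The documents leave this open.
- *EASI and SCORAD count skin that never receives gel, which caps EASI response.* Section 8.1 says only that "Eczema Area and Skin Severity Index (EASI) is a validated Investigator-administered scoring system used to measure the severity of clinical signs in AD", and it names no body area for SCORAD either. The SAP adds EASI sub-scores by localization without listing sites. The area is unstated, and inclusion of the untreated sites cannot be inferred from that.

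**Conclusion.** The conflict between criterion 5 and footnote i is real. The footnote is unworkable at screening and, read literally, gives a Day 15 reference that is not comparable with Days 29 and 43. All treatable skin was probably intended, so the harm depends on whether any site follows the footnote as written.

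The size depends on disease extent. The 7.5% holds only at the 14% BSA ceiling, and the mismatch nearly vanishes at about 1%. The shares assume a 1.9 m² patient and that only the marked 100 cm² of each target is rated; grading the whole of a larger lesion would raise them. A ratio of areas is not a score error, so no bias in the response proportion can be derived from it.

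The consequence is limited to the vIGA-AD response endpoints measured from Day 15, which are exploratory and summarized descriptively. The plain proportions at grade 0 or 1, the primary safety objective and the blinded lesional comparisons do not use this reference. The correction is still worth making, because one line removes a rule that, followed as written, gives a non-comparable reference.

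**What to change.** Rewrite footnote i to match criterion 5: at Screening and Days 15, 29 and 43, vIGA-AD is rated on the entire body apart from the scalp, palms, soles and genitals, and any new lesions in that area are included. Repeat the same area in SAP Section 3.4, where the vIGA-AD endpoints are listed. The lesional score under footnote k stays as it is.

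The cost is one footnote, one sentence in the SAP and a line of rater guidance. No visit or assessment is added.
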